7.9.1.8 Provider Experience secondary endpoint

Hypothesis

The following hypothesis will be tested:

$$H_0: p_A = p_C$$

$$H_a: p_A \neq p_C$$

Where p_A and p_C are the probability of responding extremely satisfied or satisfied in the VenaSeal™ system arm and the ETA or surgical stripping arm, respectively.

Endpoint Definition

Provider experience will be assessed post-index procedure for all treatment modalities, evaluating overall satisfaction with the procedure. The physician will be asked to record his satisfaction with the procedure based on five-point scale ranging from 'extremely satisfied' to 'extremely dissatisfied'. If the physician chooses 'extremely dissatisfied' or 'dissatisfied', options for reason of dissatisfaction include 'patient adverse event', 'patient discomfort or dissatisfaction', 'device component issue', 'procedure time', 'procedure steps', and 'other'.

Analysis Methods

The percentage of providers responding either extremely satisfied or satisfied to the provider experience question per procedure. A Fisher's exact test will be used to compare the fraction of physicians reporting 'extremely satisfied' or 'satisfied' in each arm.

Determination of Subjects for Analysis

The analysis will consist of the ITT population.

7.9.2 VLU (Single Arm) Study

Analyses will be performed on all ITT subjects in the VLU Study.

Descriptive statistics will be presented for the study endpoints. For categorical variables, the count and percentage of subjects with each outcome will be presented. For continuous variables, summary statistics (mean, standard deviation, median) will be presented. Time to-event response variables may be displayed by using a Kaplan-Meier plot or cumulative incidence curve.

7.9.2.1 Analysis of Primary Endpoint

7.9.2.1.1 Hypothesis

There is no hypothesis testing for this primary endpoint.

7.9.2.1.2 Endpoint Definition

The primary endpoint of the VLU Study is time to ulcer healing and will be measured until healing has occurred, calculated through healing confirmation and verified by an independent core laboratory through 12 months. Once the site research team has been informed of all wounds healing on the target ulceration by the wound care center, the subject will undergo an ulcer healing verification visit within 2 weeks of ulcer healing to confirm healing and collect photographs of the ulcer. The ulcer assessment core laboratory will verify healing. If core laboratory does not confirm healing with the first set of photographs, the subject will return in 1 week for additional photographs to be collected and sent to the core laboratory. If the core laboratory does not confirm healing after the second set of photographs, but the treating physician believes the ulcer has healed, the ulcer will be classified as healed.

7.9.2.1.3 Rationale for Performance Criteria

There is no performance criteria and descriptive statistics will be presented for primary endpoint.

7.9.2.1.4 Analysis Methods

As a primary analysis, the Kaplan-Meier estimate on the time to ulcer healing will be provided. The subjects who are lost to follow up or exit but have no record on the time to ulcer healing will be censored at the time of last follow-up visit. Day 0 is the day of index procedure.

The median time to ulcer healing of the primary endpoint will be assessed from survival analysis when survival exceeds 50%. The two-sided 95% confidence interval of the median time to ulcer healing will be provided using the following formula to calculate the upper and lower bounds of a confidence interval for a median²:

$$j: nq - z^* \sqrt{nq(1-q)}$$

$$k: nq + z^* \sqrt{nq(1-q)}$$

where:

- **n:** The sample size
- **q:** The quantile of interest. For a median, we will use $q = 0.5$.
- **z:** The z-critical value

The j and k are rounded up to the next integer. The resulting confidence interval is between the j th and k th observations in the ordered sample data.

If any subjects do not have an observed ulcer healing time through 12 months, their ulcer healing times will be considered to be greater than 12 months for the purpose of calculating the confidence interval for the median.

Other summary statistics may be presented describing the distribution of time to ulcer healing.

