6.2 VLU Study (Single-Arm Study)

6.2.1 Sample Size Consideration

The primary endpoint in the VLU Study is time to ulcer healing. For reference, the EVRA study evaluated clinical and cost effectiveness of early endovenous treatment and standard care vs. deferred intervention in patients with chronic venous ulceration. As there are no statistically powered hypotheses in the VLU Study, precision estimates (distance from point estimate to upper 95% two-sided confidence bound) were used to derive the sample size based on the outcomes of the EVRA study.

In comparison to the EVRA study, criteria for VLU Study inclusion are less restrictive, which may result in an ulcer population which is older and heals more slowly than the EVRA early-intervention group. Precision calculations utilized an assumed median time to healing of 70 days which is the approximate average of the median healing time between the EVRA early-intervention and deferred-intervention groups (56 and 82 days, respectively). Precision estimates for a range of sample sizes are provided in Table 5. A simulation was run 10,000 times on the assumption of exponential distribution of 70 days median time to healing. The simulation results show that a precision of less than 23 days can be obtained with a sample size of 125 subjects enrolled in the VLU Study.

Table 5: Sample Size for the VLU Study

Sample size	Evaluable Sample Size (10% attrition)	Precision
80	72	<30 days
90	81	<28 days
100	90	<26 days
110	99	<25 days
115	104	<24 days
120	108	<24 days
125	113	<23 days

7. Statistical Methods

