7.9.1.2 Analysis of Key Secondary Endpoints

7.9.1.2.1 Hypothesis

For key secondary endpoint of return to work, the following hypothesis will be tested:

$$H_0: S_A(t) = S_C(t)$$

$$H_a: S_A(t) \neq S_C(t)$$

Where $S_A(t)$ and $S_C(t)$ are the survival functions for freedom from return to work for the VenaSeal™ system arm and ETA or surgical stripping arm, respectively.

For the other key secondary endpoint of primary target vein closure rate at 6 months, the following hypothesis will be tested:

$$H_0: S_A(t) \leq S_C(t) - 10\%$$

$$H_a: S_A(t) > S_C(t) - 10\%$$

Where $t = 6$ months, and $S_A(t)$ and $S_C(t)$ are the survival functions for freedom from vessel re-opening at 6 months in the VenaSeal™ system arm and the ETA or surgical stripping arm, respectively and -10% is the non-inferiority margin.

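### SAP 7.9.2.1.4 states the condition for reporting the median ulcer healing time the wrong way round

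*SAP*

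**What the plan says.** SAP 7.9.2.1.4 sets the analysis of the VLU primary endpoint. It begins "As a primary analysis, the Kaplan-Meier estimate on the time to ulcer healing will be provided". It then gives the rule for the summary read from that curve: "The median time to ulcer healing of the primary endpoint will be assessed from survival analysis when survival exceeds 50" per cent. No time point is attached to the 50%, and the section does not define survival.

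The same section promises a two-sided 95% confidence interval for the median without any condition, built from order-statistic ranks. For that interval only, subjects with no observed healing through 12 months count as having healing times beyond 12 months.

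Three other places bear on the reading:

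- SAP 7.9.2.1.2 limits the endpoint to 12 months ("calculated through healing confirmation and verified by an independent core laboratory through 12 months").
- SAP 7.9.1.2.1 shows how the SAP uses survival when the event is a good one. For return to work, the functions "are the survival functions for freedom from return to work". SAP 7.9.1.7 does the same for return to normal activities.
- SAP 6.2.1 bases the VLU sample size on the median: "Precision calculations utilized an assumed median time to healing of 70 days", leading to the statement that "a precision of less than 23 days can be obtained with a sample size of 125 subjects".

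Protocol section 14.2 promises descriptive statistics and contains no condition of this kind.

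**The concern.** When the event is healing, the Kaplan-Meier survival curve starts at 100% unhealed and falls as ulcers heal. The median is the first time at which it is at 50% or below. If the curve is still above 50% when follow-up ends, there is no median to report. The sentence makes survival above 50% the trigger for assessing the median, which is the opposite condition.

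The affected quantity is the point estimate of the median. It matters because the precision of that median is the only basis given for the VLU sample size, and the study has no hypothesis test. The median and its interval are therefore the main numerical summary of the primary endpoint. SAP 6.2.1 also warns that this population may heal more slowly than the early-intervention group of the reference trial, so the SAP needs a clear rule for a median that is not reached. It has none for the point estimate.

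**Working it through.** **Inputs.** Exponential healing times with a median of 70 days; 125 enrolled and 113 evaluable after 10% attrition; stated precision under 23 days (all SAP 6.2.1). Follow-up of 12 months, taken as 365 days (SAP 7.9.2.1.2). Order-statistic interval with ranks rounded up (SAP 7.9.2.1.4).

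**1. Reproduce the plan's precision figure.** With n = 113 and q = 0.5:

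- j = 56.5 − 1.96 × √28.25 = 46.1, rounded up to 47
- k = 56.5 + 1.96 × √28.25 = 66.9, rounded up to 67

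In 10,000 simulated samples without censoring, the mean distance from the median to the upper bound was 19.6 days, and to the farther bound 21.5 days. Inverting a log-log interval for the survival curve gave 19.6 and 22.1 days. All are below 23, so the stated figure holds under the SAP's definition of precision (upper bound) and the protocol's (the farther bound). This calculation does not involve the 50% rule.

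**2. Survival at 12 months in the planned scenario.**

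S(365) = 0.5^(365/70) = 0.5^5.214 = 0.027

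So 2.7% remain unhealed and 97.3% have healed. The condition that survival exceeds 50% is not met.

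**3. When would the condition be met at 12 months?** For 113 evaluable subjects without censoring, this needs at least 57 unhealed at day 365. S(365) = 0.5^(365/M) for true median M, and the probability is a binomial tail. Medians other than 70 days are assumptions used to show the range; 56 and 82 days are the reference-trial values in SAP 6.2.1.

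| True median (days) | S(365) | Probability that more than half are unhealed |
|---|---|---|
| 56 | 0.011 | about 0 |
| 70 (plan) | 0.027 | about 6 × 10⁻⁵⁸ |
| 82 | 0.046 | about 0 |
| 180 | 0.245 | about 0 |
| 240 | 0.348 | 0.0005 |
| 365 | 0.500 | 0.50 |
| 400 | 0.531 | 0.75 |
| 500 | 0.603 | 0.987 |

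The condition becomes likely only when the true median is beyond 12 months.

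**4. When can the median be read?** Simulations used 125 subjects, follow-up cut at 365 days, and an assumed exponential dropout of 10% a year (2,000 runs each).

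- True median 70 days: the Kaplan-Meier median was estimable in 100% of runs, with mean 70.2 days.
- True median 500 days: it was estimable in 1% of runs.

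Steps 3 and 4 mirror each other. Where the written condition fails, the median is available; where it is met, the median is almost always not reached.

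**The case against.** The strongest defence is that the authors meant cumulative healing. SAP 4.1.2 describes this endpoint as a probability of confirmed healing, and SAP 7.9.2 allows a cumulative incidence curve for VLU time-to-event variables. If the 50% refers to the proportion healed, the condition is correct. As an account of intent this is plausible, and the sentence may well be a drafting slip. It does not rescue the text: the word used is survival, it follows directly on the Kaplan-Meier estimate, and the SAP elsewhere uses survival for freedom from a favourable event. If healing was meant, the sentence still needs changing.

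The second defence concerns reach, and it stands. A reader might infer that the rule withholds the primary estimate. It does not: the stated primary analysis is the Kaplan-Meier estimate, which is unconditional. A reader might also infer that the plan would leave nothing on the median when healing goes well. The confidence interval for the median is promised without condition and other summary statistics are allowed, so only the point estimate is caught. The slow-healing case is also partly covered, because unhealed subjects count as beyond 12 months, although that provision is limited to the interval.

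Third, standard software returns the median once the curve reaches 50%, whatever the SAP says. That is likely, but the output would then contradict the written rule. SAP section 8 requires Level I validation for primary endpoint analyses, and a validator working from the text would meet that contradiction.

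**Conclusion.** The condition is reversed under the ordinary meaning of survival and under the SAP's own usage. Read literally at 12 months, it would drop the median point estimate in the planned scenario, where 2.7% are expected to be unhealed at day 365, and ask for it when it has not been reached. The plan would then give an interval for a median whose point estimate it omits.

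The practical consequence is limited. No hypothesis test or performance criterion is affected, the Kaplan-Meier estimate and the interval for the median are produced either way, and the sample size of 125 and the precision of under 23 days stand. It would also be too strong to say that a median cannot be estimated whenever survival exceeds 50%. Every Kaplan-Meier curve begins above 50%, and the median is lost only if the curve stays above 50% to the end of follow-up.

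The 2.7% rests on the plan's exponential 70-day assumption. The alternative medians and the dropout pattern are assumptions of this check. The direction of the error depends on none of them, because it follows from the definition of a Kaplan-Meier median. A wrong rule for the quantity on which the study was sized should be corrected before analysis.

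**What to change.** Replace the sentence in SAP 7.9.2.1.4 with:

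*The median time to ulcer healing will be reported if the Kaplan-Meier probability of remaining unhealed falls to 50% or below (cumulative healing reaches at least 50%) within 12 months; otherwise it will be reported as not reached (>12 months).*

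This states the correct condition, fixes the meaning of the 50%, and supplies the missing rule for a point estimate that is not reached. It agrees with the existing treatment of unhealed subjects in the confidence interval. Reporting the 12-month healed proportion with its confidence interval as well would be a useful addition, but the correction does not need it.

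The cost is one sentence in the SAP. It needs no new data and changes neither the design nor the sample size.

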7.9.2.1.6 Missing Data Analysis

No statistical techniques will be used to impute missing data considering that time-to-event analysis will appropriately account for censoring.

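### VLU primary endpoint: the median healing time censors dropouts, but its 95% interval ranks them as unhealed beyond 12 months, so the interval shifts late and can under-cover

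*SAP*

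**What the plan says.** SAP 7.9.2.1.4 sets out the analysis in two parts.

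- **Estimate.** "As a primary analysis, the Kaplan-Meier estimate on the time to ulcer healing will be provided", and the median is read from that survival analysis. Subjects who are lost or exit and "have no record on the time to ulcer healing will be censored at the time of last follow-up visit".
- **Interval.** "The two-sided 95% confidence interval of the median time to ulcer healing will be provided using the following formula": ranks j and k equal nq minus and plus z√(nq(1−q)), with q = 0.5 and n described only as the sample size. "The j and k are rounded up to the next integer", and "The resulting confidence interval is between the j th and k th observations in the ordered sample data". For any subject whose healing was not observed by month 12, "their ulcer healing times will be considered to be greater than 12 months for the purpose of calculating the confidence interval".

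SAP 7.9.2.1.6 then states: "No statistical techniques will be used to impute missing data considering that time-to-event analysis will appropriately account for censoring". SAP 7.4 also says that dropouts in time-to-event outcomes are censored when they discontinue. SAP 7.9.2.1.5 limits the primary analysis to ITT subjects with available data. Protocol 14.2.1 and SAP 6.2.1 size the VLU Study on the precision of this interval: under 23 days with 125 enrolled and 113 evaluable after 10% attrition.

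**The concern.** The rank formula is valid when every healing time is known, or known to lie beyond the ranks used. It has no term for censoring. The rule that makes it computable treats two kinds of subject alike:

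- those followed to 12 months unhealed, whose time really is beyond 12 months;
- those who left earlier, whose time is unknown.

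The second group is censored in the median and assumed unhealed for a year in the interval, so the statement in SAP 7.9.2.1.6 about censoring does not hold for the interval.

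The VLU Study has no hypothesis test. The median with its 95% interval is the main statement of uncertainty for its primary endpoint, and the sample size was justified by that interval's width. If the rule is applied as written, the reported limits depend on how many subjects left unhealed and how early, and a reader cannot tell this from the result.

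**Working it through.** **Inputs.** Exponential healing with median 70 days, so λ = ln 2/70 = 0.00990 per day; 125 enrolled, 113 evaluable, 10% attrition (SAP 6.2.1, protocol 14.2.1). z = 1.96 and the rank rule come from SAP 7.9.2.1.4. The documents do not say when dropouts leave, so timing is an assumption and a range is shown.

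**1. The plan's own figure.** For n = 113, the ranks are 56.5 ± 1.96√28.25 = 46.08 and 66.92, rounded up to 47 and 67. In 10,000 samples without censoring, the mean distance from the median to the farther limit (the protocol's definition) is about 21.6 days, and to the upper limit (the SAP's definition) about 19.8 days. Both agree with the stated bound of 23 days. The other rows of the table also reproduce. The plan's figure is therefore matched by a calculation without censoring, which does not test the rule for dropouts.

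**2. Coverage of the rank interval with dropouts.** For n = 125, the ranks are 62.5 ± 1.96√31.25 = 51.54 and 73.46, rounded up to 52 and 74. The interval contains 70 days exactly when the number of subjects observed to heal by day 70 is between 52 and 73. That number is binomial with n = 125 and

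p = (1 − d) × 0.5 + d × g,

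where d is the share who drop out and g is the chance that a dropout is seen to heal by day 70 before leaving. If leaving is uniform over 0 to W days:

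- W = 30: g = 1 − (1 − e^(−30λ))/(30λ) = 0.135
- W = 90: g = [70 − 0.5/λ + 20 × 0.5]/90 = 0.328
- W = 365: g = [70 − 0.5/λ + 295 × 0.5]/365 = 0.458

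Solving (1 − d)F(t) + d·g(t) = 0.5, where F(t) = 1 − e^(−λt) and g(t) is g with day t in place of day 70, gives the time around which the interval is really centred.

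| Dropout | p | Exact coverage | Centre (true median 70) |
|---|---|---|---|
| none | 0.500 | 95.1% | 70.0 d |
| 10% over 365 days | 0.496 | 95.0% | 70.9 d |
| 10% within 90 days | 0.483 | 93.5% | 73.9 d |
| 10% within 30 days | 0.464 | 87.3% | 78.5 d |
| 20% over 365 days | 0.492 | 94.7% | 71.8 d |
| 20% within 30 days | 0.427 | 63.1% | 90.4 d |

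**3. Simulation against a Kaplan-Meier interval.** Thousands of simulated trials per scenario, n = 125. The comparator inverts the Greenwood test on the log-log scale (Brookmeyer-Crowley type).

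| Dropout | SAP interval (days) | SAP coverage | Kaplan-Meier interval (days) | Kaplan-Meier coverage |
|---|---|---|---|---|
| none | 53.6–89.3 | 95% | coincides | 95% |
| 10% over the year | 54.0–91.1 | 94.8% | about 53–89 | about 95% |
| 10% actually lost unhealed (constant hazard) | 55.6–96.4 | 94.0% | 52.6–89.2 | 94.8% |
| 10% within 90 days | 56–97 | 93% | 53–89 | about 95% |
| 10% within 30 days | 58.7–102.1 | 87.1% | 52.2–89.2 | 94.6% |
| 20% within 30 days | 66.6–122.2 | 63.5% | 51.7–90.7 | 95.2% |

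The misses are one-sided. With 10% lost unhealed, the SAP interval lies wholly above 70 days in 4.9% of trials and wholly below in 1.1%. With 10% lost within 30 days, the figures are 12.5% and 0.4%. In those two cases the typical distance from the Kaplan-Meier median to the SAP upper limit is 25.8 and 31.7 days (18.7 and 18.9 with the Kaplan-Meier interval), against the planned 23. With 20% lost within 30 days, the Kaplan-Meier median falls below the SAP interval's own lower limit in 11% of trials.

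**The case against.** Five points can be made for the plan.

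- **Timing.** The plan gives 10% attrition but no timing, and nothing in it suggests that all loss falls in the first month. VLU subjects count as enrolled only once the device enters the body, so there is no enrolled-but-untreated group. Loss after healing does not touch this endpoint: 10% dropout at a constant hazard leaves only 2.8% lost unhealed, and coverage is then 95.1%. This stands. The 30-day rows are stress cases, and the 20% row also doubles the planned attrition.
- **Available data.** The restriction in SAP 7.9.2.1.5, and an n that is not spelled out, could remove subjects with no follow-up at all and so soften the early-loss case. That is fair, but dropouts with any follow-up would still be ranked beyond 12 months.
- **Intended scope.** The rule may have been meant only for subjects followed unhealed to 12 months, for whom it is correct. The wording covers any subject without an observed time. On the narrower reading, the SAP has no rule for ranking dropouts, so the section still needs correcting.
- **Descriptive endpoint.** No success claim depends on the interval, the Kaplan-Meier estimate itself is unaffected, and the shift does not flatter the device. This limits the consequence, but the reported limits are still wrong.
- **Conservatism.** If dropouts truly would not heal, ranking them late would be less wrong. The Kaplan-Meier median would then be the biased part, and the two would still disagree.

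**Conclusion.** The concern holds. The inconsistency is in the text: one section censors dropouts for the median and treats them as year-long non-healers for its interval, against SAP 7.4 and 7.9.2.1.6. Every dropout pattern examined moves both limits later.

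How much this matters depends on timing that the documents do not give. At the planned 10%, loss spread over the year costs 1 to 2 days and almost no coverage. Loss concentrated early costs up to about 6.5 days on the lower limit and 13 on the upper, with coverage down to 87%. These figures assume exponential healing with a 70-day median, 125 subjects in the calculation, and dropout unrelated to healing. Confidence is high in the mismatch and its direction; the coverage loss is conditional on early or heavier dropout.

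**What to change.** In SAP 7.9.2.1.4, delete the rank formula and the rule placing unobserved times beyond 12 months. Specify instead the Kaplan-Meier-based 95% interval for the median (Brookmeyer-Crowley, log-log transformation), with dropouts censored at last follow-up and subjects still unhealed at 12 months censored there. The statement in SAP 7.9.2.1.6 then becomes true of the interval as well as the estimate. If the sponsor wants a view in which every dropout counts as unhealed, keep the rank interval as a labelled sensitivity analysis and report how many subjects it affects.

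The cost is SAP wording only. SAS PROC LIFETEST reports this interval with the median, and data collection, sample size and trial conduct do not change.
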